#### **Data Management**

Describe how and who manages confidential data, including how and where it will be stored and analyzed. For instance, describe if paper or electronic report forms will be used, how corrections to the report form will be made, how data will be entered into any database, and the person(s) responsible for creating and maintaining the research database. Describe the use of pseudonyms, code numbers and how listing of such identifiers will be kept separate from the research data.

Written personal identifying information concerning study participants will be kept to a minimum. A master list of study participants that includes the assigned ID#, the first and last names, and any project-necessary grouping designations (e.g., control vs. experimental group) maintained for tracking purposes is stored in password-protected administrative databases only on the PI's server and kept in locked filing cabinets in her office. Screening forms and interview cover sheets only include identifying information this is necessary. All of this information is confidential and kept in a locked file cabinet separate from study data. Any information with subject identification that is not needed must be shredded. Computer files used for the purpose of tracking study participants are set up with password protection. Access to these files is restricted to defined key personnel.

#### **Radiation Exposure\***

Are research subjects receiving any radiation exposure (e.g. X-rays, CT, Fluoroscopy, DEXA, pQCT, FDG, Tc-99m, etc.) that they would not receive if they were not enrolled in this protocol?

No

#### **Human Source Material\***

Does this research include collection or use of human source material (i.e., human blood, blood products, tissues or body fluids)?

Yes

#### **CACTIS and CT Studies\***

Does the research involve Center for Advanced Computed Tomography Imaging Services (CACTIS) and CT studies that research subjects would not receive if they were not part of this protocol?

No

#### **CAMRIS and MRI Studies\***

Does the research involve Center for Advanced Magnetic Resonance Imaging and Spectroscopy (CAMRIS) and MRI studies that research subjects would not receive if they were not part of this protocol?

No

**Cancer Related research not being conducted by an NCI cooperative group\***

Does this protocol involve cancer-related studies in any of the following categories?

No

**Medical Information Disclosure\***

Does the research proposal involve the use and disclosure of research subject's medical information for research purposes?

No

**CTRC Resources\***

Does the research involve CTRC resources?

No

**If the answer is YES, indicate which items is is provided with this submission:**

**Use of UPHS services\***

Does your study require the use of University of Pennsylvania Health System (UPHS) services, tests or procedures\*, whether considered routine care or strictly for research purposes?

No

**Primary Focus\***

Sociobehavioral (i.e. observational or interventional)

**Protocol Interventions**

Sociobehavioral (i.e. cognitive or behavioral therapy)

**Drug**

**Device - therapeutic**

**Device - diagnostic (assessing a device for sensitivity or specificity in disease diagnosis)**

**Surgical**

**Diagnostic test/procedure (research-related diagnostic test or procedure)**

**Obtaining human tissue for basic research or biospecimen bank**

**Survey instrument**

**None of the above**

**The following documents are currently attached to this item:**

*There are no documents attached for this item.*

## **Sponsors**

**Business Administrator**

none

**Department budget code**

000 - 000 - 0 - 000000 - 0000 - 0000 - 0000

**Funding Sponsors**

Name:	NATIONAL INSTITUTE OF NURSING RESEARCH/NIH/DHHS
Type:	UPENN Federal

**Funding sponsors billing address**

If you have selected a commercial or industry sponsor, please provide the appropriate address and contact information for the Sponsor for the purposes of billing for IRB review fees (initial review, continuing review and convened modification fees apply here). If the Sponsor is not industry/commercial, this information is not necessary to provide with your application.

**Funding sponsors gift**

Is this research being funded by a philanthropic gift?

No

***Regulatory Sponsor*****IND Sponsor**

none

000 - 000 - 0 - 000000 - 0000 - 0000 - 0000

**Industry Sponsor**

None

**Project Funding\***

Is this project funded by or associated with a grant or contract?

Yes

***Selected Proposals***

Proposal No	Title
10057075-01	The Role of Palliative Care Interventions to Reduce Circadian Rhythm Disorders in Persons with Dem...

**Sponsor Funding**

Is this study funded by an industry sponsor?

No

**Status of contract****The following documents are currently attached to this item:**

*There are no documents attached for this item.*

## Multi-Center Research

**Penn as lead**

1. Is this a multi-center study where Penn is serving as the Lead Site or the Penn PI is serving as the Lead Investigator?

No

**Management of Information for Multi-Center Research****Penn irb of record**

2. Is this a multi-center study where the Penn IRB will be asked to serve as the IRB of Record for other external study sites?

No

***Other Sites***

No other sites

# Protocol

## Abstract

Over 5 million Americans have Alzheimer's disease or a related dementia, a progressive and fatal neurodegenerative condition, affecting close to 15 million family caregivers (CG). Circadian rhythm disorders (CRDs) occur in the majority of persons with dementia and include late afternoon/evening agitation and irregular sleep-wake rhythms such as daytime hypersomnia, frequent night awakenings, and poor sleep efficiency. CRD symptoms pose a great burden to CG, and are the principal causes of distress, poor QOL, and institutionalization. Regulating the circadian system through the use of light and activity has been shown to alter core clock processes that drive CRD symptoms and suggests that a combination of cognitive, physical and sensory-based activities, delivered at strategic times, may be an effective mechanism through which to reduce CRD symptoms. To date, there are no trials linking the nature and timing of activities with key palliative and biobehavioral outcomes. We propose a definitive Phase III efficacy trial of the Healthy Patterns intervention, a home-based activity intervention designed to improve CRDs and QOL that builds on our pilot work. We will use a randomized two-group parallel design of 200 people with dementia and their CGs (dyads) assigned to the Healthy Patterns intervention or a control intervention of equivalent in-home attention and social contact. The success of the intervention will be determined by its impact on palliative outcomes including measures of QOL as well as actigraphic and proxy reported measures of CRD symptoms. CG outcomes of interest will be burden, subjective sleep quality, and QOL.

## Objectives

### Overall objectives

We propose a definitive Phase III efficacy trial of the Healthy Patterns intervention, designed to improve sleep disturbance symptoms and QOL, that systematically builds on our pilot work demonstrating feasibility, safety and potential benefits. We will use a randomized, two-group, parallel design of 200 persons with dementia (PWD) and their family caregivers (dyads) assigned to the Healthy Patterns intervention or an attention control intervention of equivalent in-home attention and social contact. Specific components of this brief, one-month, eight session, home-based intervention include: 1) assessing PWD health/functional status and preferences/interests; 2) educating caregivers on environmental cues to promote activity and sleep; and 3) training of CG in using timed morning, afternoon, and evening activities based on circadian needs across the day. The patient focused outcomes of interest are QOL, and indices of sleep as measured by objective and subjective indicators including actigraphy, subjective sleep quality, and assessment of neuropsychiatric symptoms. Caregiver outcomes of interest are QOL, burden, confidence using activities, and sleep disruption. The specific aims for this study are to test: 1. The immediate (at 1 month) and sustained (at 4 months) effect of the Healthy Patterns activity intervention on PWD quality of life and CRD symptoms. Hypothesis 1a. Compared to control group participants, PWD receiving the intervention will demonstrate quality of life, total sleep time, nocturnal wake after sleep onset, day/night sleep ratio, and neuropsychiatric symptoms at 1 month. Hypothesis 1b. Compared to control group participants, PWD subjects receiving the intervention will demonstrate quality of life, total sleep time, and neuropsychiatric symptoms at 4 months. 2. The immediate (1 month) and sustained (4 months) effect of the Health Patterns activity intervention on caregiver outcomes. Hypothesis 2a. Compared to control group participants, caregivers who have received the intervention training will demonstrate quality of life, burden, confidence in using activities, and sleep disruption at 1 month. Hypothesis 2b. Compared to control group participants, caregivers who have received the intervention training will demonstrate quality of life, burden, confidence in using activities, and sleep disruption at 4 months. 3. The mediating effect of neuroendocrine activity on changes in CRD symptoms. Hypothesis 3. CRD symptoms will be mediated by changes in diurnal cortisol from baseline to 1 month.

### Primary outcome variable(s)

Symptoms of sleep disruption as measured by actigraphy Neuropsychiatric symptoms

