All measures to be used in the study are established indexes. No new or novel instruments will be used. Quality of life in persons with dementia will be assessed using two well established measures the QOL-AD and the PHQ-9. The dementia-specific 13-item Quality of Life in Alzheimer's Disease scale reflects multiple dimensions (physical, social, emotional, and functional well-being) with each rated as 1=poor, 2=fair, 3=good, or 4=excellent. A total score representing the sum of items ranging from 13 to 52 will be derived separately for persons with dementia and the family caregivers (CG). In addition, CG will be asked to complete the PHQ-9. Persons with dementia will be administered the MMSE. Other instruments include the MMSE, the Barthel Index, Cognitive status will be measured at baseline using the Mini Mental State Exam (MMSE) Physical function will be measured at baseline using the Barthel Index. Neuropsychiatric symptoms will be measured using the Neuropsychiatric Inventory (NPI) Sleep disturbance will be assessed using the PROMIS Sleep Related Impairment index. Neuroendocrine activity in persons with dementia will be assessed using the biological signature of the HPA response via salivary cortisol. CG will be instructed to collect assays at the awakening challenge and at 3 additional intervals (30 minutes after waking, mid day, and at bedtime one hour after dim light exposure). Caregivers will be provided all materials and marked plastic bags to freeze samples until pick up by the trained data collector. Caregivers will be asked to collect saliva for 2 consecutive days prior to the first study visit, and again after the last intervention visit. Sleep-wake activity will be measured using an actigraphy bracelet worn by the person with dementia. The Motionlogger actigraph, which is manufactured by AMI and utilize the same algorithm as used in earlier studies of community dwelling persons with dementia, will be placed on the non-dominant wrist at baseline and will be worn for consecutive 24 h-periods until removal at 1 month (T2) data collection. Actigraphs will be set to collect data in 60-second epochs via tri directional accelerometer using a validated algorhythm. The primary measure of interest will be number of minutes of wake after sleep onset (WASO). Other parameters that will also be subject to analysis include total sleep time (TST), day/night sleep ratio, and number of night awakening. There will NOT be any remote monitoring or data transfer with the actigraph through a wireless connection.

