**Analysis Plan**

Sample Size: Sample size calculations are based on our ability to detect a medium effect size (d) of 0.45; and d) a type I error rate of .05. Our projected effect size is justified for two reasons. First, clinical trials on symptoms of CRD use this effect size as an indication of clinical significance. Second we were able to achieve large treatment effects across outcomes in the pilot phase- although we acknowledge that effect sizes may be overly optimistic in pilot studies. To attain 80% power for a two-sided comparison of the two treatment groups at 1 month will require 78 dyads per group (Aim 1 and 2). We plan to recruit an additional 22 per group or 100 dyads for a total of 200 allowing for 22% attrition by 4 months (Aim 3). The statistical power for secondary analyses at 3 months will be the same as for the primary; 80% for a 0.45 effect size with 5% two-tailed tests. Analysis of aims: First, we will conduct

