descriptive analyses and univariate comparisons of the experimental and control intervention group conditions. We will use Chi-square, Wilcoxon rank-sum tests, and independent groups t-tests as appropriate to identify any differences between experimental and control group participants at baseline. In addition to serving as a final data quality check, these analyses will be used to characterize our study population, assess the success of randomization in balancing the two groups and determine the impact of any dropouts on group balance. Aim 1: to test the timed activity intervention on patient CRD symptoms and QOL. Our primary analysis will examine the effect of the timed intervention compared to the attention control condition based on "intention to treat" (ITT). Data from all dyads randomized to the experimental group will be part of analyses regardless of actual number of completed intervention sessions. We will test the normality assumption for the primary CRD outcome measure (WASO) and for the other dependent measures (TST, neuropsychiatric symptoms; QoL) by examining the distribution of residuals after standard parametric comparisons. If the residual distribution is markedly skewed, we will examine whether data transformations are sufficient for improving the fit of the data to the normality assumption. Aim 1: To analyze the effects of the timed intervention on our primary outcomes difference scores (T2-T1) will be calculated for each participant and these change scores will be analyzed as a function of the treatment group, with the baseline observation (T1) serving as a covariate. Other potential covariates measured at baseline (e.g., age, education) will also be evaluated as potential predictors of change in outcome, and included as additional covariates of the intervention effect as indicated. Aim 2: To test the effect of the timed activity intervention on caregiver outcomes. For Aim 2, we follow the approach for Aim 1 by examining group differences in the baseline-adjusted change scores (T2-T1; T3-T1) for CG outcome measures of burden and intent to institutionalize. Aim 3: To test the mediating effect of patient HPA axis activity on symptoms of CRD. We will test mediation by modeling the measures of baseline-adjusted changes in CRD symptoms (WASO, TST, neuropsychiatric symptoms) in nested analytic models that either do or do not include the proposed mediator (T2-T1 change in saliva cortisol). Using nested regression models, estimates will be obtained of 1) the effect of the intervention on baseline-adjusted change in cortisol, 2) the effect of the change in cortisol on baseline-adjusted change in WASO (or other outcomes), 3) the effect of the intervention on baseline-adjusted WASO before adding change in cortisol to the model, and 4) the effect of the intervention on baseline-adjusted WASO after adding change in cortisol to the model. These path estimates are often referred to by the letters a, b, c, and c' in the mediation literature. The product of the a and b estimates (a\*b) represents the mediated effect, and this will be tested for statistical significance using the standard Sobel method or with bootstrapping techniques. The proportion of the total effect (c) that is explained by mediation (a\*b) will also be calculated and tested for significance. Mediation models for data from two-wave randomized trials can provide substantially different results depending on whether change scores are used and whether baseline covariate adjustments are implemented. Our approach will capitalize on this recent methodological work and provide sensitive analyses that determine whether the interventions impact on 1-month change in CRD symptoms is partly due to its effect on 1-month change in cortisol secretion.

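### The primary outcome set and success rule are not fixed: two primaries are listed, the analysis plan singles out WASO, and the sample size fits one test at 0.05

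*Combined protocol and SAP*

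**What the plan says.** **Primary outcome variable(s)** lists "Symptoms of sleep disruption as measured by actigraphy Neuropsychiatric symptoms". **Secondary outcome variable(s)** lists quality of life.

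**Study Instruments** settles the actigraphy parameter: "The primary measure of interest will be number of minutes of wake after sleep onset (WASO". It measures neuropsychiatric symptoms with the NPI.

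**Analysis Plan**, on Aim 1, describes normality checks "for the primary CRD outcome measure (WASO) and for the other dependent measures (TST, neuropsychiatric symptoms; QoL". It then says that for "our primary outcomes difference scores (T2-T1) will be calculated for each participant", "with the baseline observation (T1) serving as a covariate". Those primary outcomes are not listed.

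**Analysis Plan**, Sample Size, assumes "a medium effect size (d) of 0.45; and d) a type I error rate of .05" and states: "To attain 80% power for a two-sided comparison of the two treatment groups at 1 month will require 78 dyads per group". Recruitment is inflated to 100 per group, "for a total of 200 allowing for 22% attrition by 4 months". The calculation names no outcome.

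**Abstract** makes success depend on QOL together with actigraphic and proxy-reported CRD measures. **Overall objectives**, Hypothesis 1a, lists five patient outcomes at 1 month without ranking them.

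No visible section states an alpha split, a testing order, or whether one or both primaries must be significant.

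**The concern.** The trial is presented as a definitive Phase III efficacy trial, so a reader must be able to tell in advance which result makes it positive. At present that depends on the section followed. If WASO improves and NPI does not, the trial is positive with WASO as sole primary, positive or not with two primaries depending on an unstated rule, and unclear under the Abstract, which brings in QOL. If NPI improves and WASO does not, the readings diverge again.

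The stated 5% error and 80% power also belong to one test. With two primaries, what happens to them depends on how the two results are combined. That choice is not credible once results by arm have been seen.

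**Working it through.** **Inputs.** From Analysis Plan, Sample Size: d = 0.45, two-sided alpha 0.05, power 80%, 78 evaluable dyads per group, 22% attrition, 100 recruited per group. Assumed, because the documents give neither: correlation r between the two endpoints from 0 to 0.9, and d = 0.45 on both.

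**1. The plan's own figure.** n per group = 2(1.960 + 0.842)² / 0.45² = 77.5, so 78. Then 78 / (1 − 0.22) = 100. Both figures reproduce for one endpoint at the full 0.05. The exact two-sample t-test with 78 per group has power 0.7975. At 0.025 the same test has power 0.7074. The calculation therefore contains no allowance for a second primary.

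**2. Either wins, each at 0.05.** With r = 0 the error is 1 − 0.95² = 0.0975. From the bivariate normal:

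| r | 0 | 0.3 | 0.5 | 0.7 | 0.9 |
|---|---|---|---|---|---|
| Overall error | 9.75% | 9.5% | 9.1% | 8.4% | 7.0% |

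**3. Both must win, each at 0.05.** No alpha split is needed. With r = 0 the power at 78 per group is 0.7975² = 0.636. Simulation gives 0.684 at r = 0.5 and 0.746 at r = 0.9, so about 64% to 75%.

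**4. Holm at overall 0.05.** The smaller p-value is tested at 0.025 and, if significant, the larger at 0.05. At 78 per group and r = 0:

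- Power per endpoint: 0.7074 + (0.7975 − 0.7074) × 0.7074 = 0.771.
- At least one win: 1 − (1 − 0.7074)² = 0.914.
- WASO, if NPI does not respond: 0.7074 + 0.0901 × 0.025 = 0.710.

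Over r = 0 to 0.9, simulation gives 77% to 75% per endpoint, 91% to 77% for at least one win, and about 71% for WASO if NPI does not respond.

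**5. Baseline adjustment.** The Analysis Plan uses T1 as a covariate but does not say whether d = 0.45 is on the raw or the adjusted SD. If it is on the raw SD and the T1–T2 correlation is 0.5 (both assumed), the effective d is 0.45 / √(1 − 0.5²) = 0.520. At 78 per group, power for both to win becomes about 80% to 86%, and Holm per endpoint about 89% to 86%.

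**6. More evaluable dyads.** The 22% attrition is by 4 months, so 78 is a floor for the 1-month comparison. If all 100 per group were evaluable, unadjusted power would be 79% to 85% for both to win, and 87% to 85% per endpoint with Holm.

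**The case against.** The best defence is that the sections can be read together. The primary field names two domains, Study Instruments picks WASO within actigraphy, and the sentence that defines the analysis uses the plural. The phrase that seems to demote neuropsychiatric symptoms occurs in a sentence about checking residuals, not one ranking endpoints. On that reading there are simply two primaries.

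Part of this stands: the wording is ambiguous rather than two flatly opposed rules. It does not close the gap. The same Analysis Plan counts neuropsychiatric symptoms among CRD symptoms under Aim 3, so calling WASO the primary CRD measure can also be read as ranking them below it. And if there are two primaries, the trial has no rule for combining them and a sample size built for one test.

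It is also fair to say that the size of the problem is conditional. No section adopts an either-wins rule at 0.05 each, so a reader who infers that the trial's error rate is 9.75% goes beyond the documents. Likewise, a firm conclusion that the trial is underpowered is not supported, because baseline adjustment or more evaluable dyads could restore 80%. Nor is the sample-size arithmetic wrong; it reproduces. Finally, the documents do not favour one multiplicity rule over another, so no single method can be called the required one.

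Table 1 of the procedures is uploaded separately and not visible. The protocol describes it as covering variables, testing occasions and sources, so it is unlikely to hold a decision rule.

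**Conclusion.** The point holds as a gap in specification with measurable consequences. With the two primaries as listed, the plan does not show that it delivers both its 5% error and its 80% power:

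- either wins at 0.05 each: overall error 9.75% to 7.0%;
- both must win: error controlled, unadjusted power about 64% to 75% at 78 per group.

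These ranges rest on assumed correlations of 0 to 0.9; the power range also assumes d = 0.45 on both outcomes and unadjusted t-tests. If WASO is the sole primary, the sample-size section is coherent as written, and the error lies in the primary-outcome field. Under either reading some text must change, and the Abstract's inclusion of QOL in the success statement conflicts with its secondary status. Because the headline conclusion depends on the answer, this must be fixed before results by arm are seen.

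**What to change.** Issue one dated amendment before any comparison by arm, and say so in it. Current Status of Study reports 170 enrolled, 0 in intervention and 35 in follow-up only, so most 1-month data probably exist already. Group designations are held in the master list on the principal investigator's server. If the statement cannot be made, the amendment should disclose that the rule was set afterwards.

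The amendment should reconcile the Abstract, Primary outcome variable(s) and both parts of the Analysis Plan by naming the primary set at T2 and one success rule with overall two-sided error 0.05. Any of these is acceptable:

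- **(a)** WASO is the sole primary at 0.05 and neuropsychiatric symptoms become secondary. The sample-size section is unchanged.
- **(b)** WASO and NPI are two primaries tested with Holm at overall 0.05. The claim covers only the outcome or outcomes that are significant.
- **(c)** Both are required, each at 0.05.

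Under (b) or (c), name the NPI score, restate the power for that rule, and say whether d = 0.45 is on the raw or the baseline-adjusted SD. The unadjusted and adjusted figures in the working show how much that matters; neither set should be copied in without that statement.

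Align the Abstract's success statement with the chosen set, and keep QOL secondary.

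The cost is one amendment and text edits, with no extra participants or measurements. The downside under (b) or (c) is a stated power that may fall below 80%; under (b) it is about 71% for WASO, unadjusted, if NPI does not respond.
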